An "intention-to-treat" approach will be used in the statistical analyses, so that data from all subjects will be included regardless of subject eligibility or adherence to the protocol. The intent-to-treat (ITT) population is defined as all subjects who received at least one dose of medication and at least one evaluation at the start of double-blind treatment irrespective of compliance and protocol violations.

An "efficacy evaluable" population will be determined based on blinded application of protocol criteria, and a statistical assessment of this group will also be performed, and 80% or greater medication compliance and no major protocol violations will be required for a subject to be "efficacy evaluable." Repeated measures mixed models (MIXED) from SPSS will be used to deal with missed data.

Demographics and Baseline Characteristics

Demographic and baseline characteristics will be summarized by treatment, and simple comparisons of the mean numerical values of these characteristics between memantine and placebo groups will be performed using the two-tailed unpaired t test. Comparability of treatment groups at baseline will be tested for the efficacy parameters in the analysis of efficacy.

Efficacy Parameters

The two primary efficacy endpoints are the comparison of the effects of memantine and placebo on the California Verbal Learning Test II short form (CVLT-II short form). The CVLT-II short form score range is 0 to 36; the baseline and post-intervention scores of the participants

HRP-503BIO	503BIO TEMPLATE: Biomedical Protocol			
Approved:	05/11/2018	Prior Version:	1/23/2018	

with Down syndrome in our pilot study (Boada et al., 2012; APPENDIX 6) were 14.53 ± 1.80 and 20.12 ± 2.10 (mean \pm SEM), for the memantine arm, compared to 16.26 ± 1.82 and 13.74 ± 1.63 , for the placebo arm of the trial. (Higher score indicates better performance.) This measure is dependent on the functional integrity of temporal lobe structures such as the hippocampus. Improvement in performance in this measure is expected to be correlated to improvements in the individuals' ability to acquire skills requiring the use of declarative memory. Ultimately, in case we are able to confirm that the administration of memantine is indeed efficacious in improving this cognitive measure in this population, such gains may lead to a measurable improvement in the quality of life of persons with Down syndrome.

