HRP-503BIO	TEMPLATE: Biomedical Protocol		
Approved:	05/11/2018	Prior Version:	1/23/2018

No direct benefit

2. If no direct benefit, state the potential benefit to society or others. Do not list compensation.

This is a study of the efficacy and safety of memantine HCl in adolescents and young adults with Down syndrome. Although specific risks have been identified above, as with any medication, it must be emphasized that serious adverse experiences, previously identified or not, may occur. Subjects participating in this study cannot be guaranteed a clinical benefit from the administration of the test drug. Thus, for each subject, the possibility of a positive therapeutic effect and their contribution to the scientific understanding of the properties and actions of memantine HCl in persons with Down syndrome are the only benefits.

Withdrawal of Research Participants

1. Describe the anticipated circumstances under which research participants will be withdrawn from the research without their consent.

Adolescents and adults with Down syndrome will be assessed by an additional experienced physician who will have the ability to discontinue the participation of a subject with Down syndrome if she/he deems this person not fit to participate fully in the trial. Although this will not necessary exclude an individual from participating in the trial, inability to complete the neuropsychological test battery would raise a red flag in terms of the fitness of an individual to participate. At all times, the research staff will assess dissent to participate in the study, and can recommend that a participant be excluded from the study because of any significant, real or perceived, discomfort expressed by the participant or parent/caregiver.

In accordance with the Declaration of Helsinki, subjects have the right to withdraw from the study at any time for any reason. The Investigators also have the right to remove subjects from the study. Subjects may be removed from the study for the following reasons:

- a. Adverse experience
- b. Intercurrent illness that, in the judgment of the Investigators, might place the subject at risk or invalidate the study
- c. Request of the subject, his/her legal representative, or Investigators, whether for administrative or other reasons
 - d. Non-compliance with medication, protocol violation, or unreliable behavior

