 - 2. Describe the procedures that will be followed when research participants withdraw or are withdrawn from the research, including partial withdrawal from procedures with continued data collection.

If for some reason the subject withdraws or is withdrawn from this study prior to Visit 5, he/she will be asked to return to the clinic for a "Treatment Discontinuation Visit." In addition, if the subject discontinues the medication prior to the end of the study, he/she will be asked to complete a "Retrieved Dropout Visit" on the date that should have represented Visit 5. Study

HRP-503BIO	TEMPLATE: Biomedical Protocol		
Approved:	05/11/2018	Prior Version:	1/23/2018

medication will not be provided beyond the study period. The procedures for the "Treatment Discontinuation Visit" will be the same as those described for "Visit 5 (Second follow-up medical visit)."

Alternatives to Participation

- 1. Please list other available clinical treatments. There are no alternative clinical treatments.
- 2. Please state if a subject could continue on standard of care therapy and what that might include.
 - Standard therapies include physical, speech, and occupational therapies, and should continue during the study.
- 3. If not a clinical trial you may state that the alternative is not to participate. If there is a viable alternative you must list it in the consent.

 N/A

Costs to Research Participants

- ☐ There are no costs to research participants or their insurance companies *please leave the rest of this section blank*
 - 1. If applicable, describe what costs the research participants will be responsible for because of participation in the research including but not limited to: transportation to study visits, parking for study visits, costs of procedures, lost, broken or stolen devices, costs of drugs or therapy, etc.

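### Removal for non-adherence can leave the primary ITT analysis without week-16 CVLT-II scores, because no post-withdrawal visit is stated to collect them

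*Combined protocol and SAP*

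**What the plan says.** **Removal.** Under Withdrawal of Research Participants, the protocol states: "Subjects may be removed from the study for the following reasons". The fourth reason listed, (d), is "Non-compliance with medication, protocol violation, or unreliable behavior". The last term is not defined.

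**Analysis sets.** Under Study Populations, the analysis is to be intention-to-treat, "so that data from all subjects will be included regardless of subject eligibility or adherence to the protocol". The ITT set needs one dose and "at least one evaluation at the start of double-blind treatment irrespective of compliance and protocol violations". Adherence enters only through a second, efficacy-evaluable set: "80% or greater medication compliance and no major protocol violations will be required for a subject to be" in that set.

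**After withdrawal.** The provision reads "If for some reason the subject withdraws or is withdrawn from this study prior to Visit 5", and asks such a person to attend a Treatment Discontinuation Visit, whose procedures are those of Visit 5. A person who stops medication early is also asked to attend a Retrieved Dropout Visit "on the date that should have represented Visit 5". No procedures are listed for that second visit.

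**Primary outcome.** The visit descriptions and Table 1 place the CVLT-II at Visit 2 (baseline) and Visit 4 (week 16) only. The Visit 5 list is medical and has no neuropsychological test. Under Statistical Models, the dependent variable is change from baseline, with the baseline value as covariate.

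**Replacement.** Either member of an age-gender matched pair may be replaced up to the end of 16 weeks on medication. The stated exception is dropout for a severe adverse event once medication has started.

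**The concern.** Reason (d) describes the participants an ITT analysis is meant to keep: those who did not take the drug as planned or did not follow the protocol. Whether someone meets (d) is settled after randomisation, partly by investigator judgement. If these people leave before Visit 4 without a CVLT-II score, those who remain are selected on adherence.

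Two things are at stake. The primary estimate may drift from the effect of assigning memantine toward its effect in people who take it. In addition, the plan has two analysis sets so that one can be read against the other. If the same people's outcomes are missing from both, agreement between the two results is less informative. Outcomes that were never collected cannot be recovered at the analysis stage.

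**Working it through.** **Step 1. Follow a participant removed under (d) at week 8.** Visit 3 is the only scheduled compliance check well before the primary assessment; the next is at Visit 5, in week 16.

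| Question | Answer in the documents |
|---|---|
| Still in the ITT set? | Yes: dosed, and evaluated at the start of treatment |
| CVLT-II before removal? | Baseline only |
| CVLT-II at the Treatment Discontinuation Visit? | No: it follows Visit 5, which has none |
| CVLT-II at the Retrieved Dropout Visit? | Not stated |
| May be replaced? | Yes, unless the dropout was for a severe adverse event |
| Change score for the model? | None, unless the CVLT-II is obtained in a way the plan does not describe |

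With one post-baseline assessment, the mixed model has no intermediate value to draw on. It conditions on arm and baseline score, not on adherence. In effect it treats the missing participant as similar to those with the same arm and baseline who stayed.

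**Step 2. Illustrative upper case for bias.** The plan gives no figure for this. The 4-point difference comes from Sample Size; the rest is assumed. Let a fraction p in each arm be non-compliant, with an effect of 4 points in compliers and 0 in non-compliers, and let all non-compliers be removed.

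- ITT effect with everyone measured = 4 × (1 − p)
- Estimate from those remaining = 4
- Overstatement = 1/(1 − p) − 1

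| p | ITT effect | Estimate | Overstatement |
|---|---|---|---|
| 5% | 3.8 | 4.0 | 5.3% |
| 10% | 3.6 | 4.0 | 11.1% |
| 20% | 3.2 | 4.0 | 25.0% |

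If only half of the non-compliers are removed, the estimate is 4(1 − p)/(1 − p/2) and the overstatement is 1/(1 − p/2) − 1, which is 2.6%, 5.3% and 11.1%. For scale, the pilot lost 3 of 40 (7.5%) for all reasons together.

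**Step 3. Effect of full follow-up on power.** The stated 99.9% power at 100 per group cannot be reproduced, because the SD of change is not given. In an unpaired comparison it needs an SD of about 5.6. The pilot SEMs (n = 18, and 37 − 18 = 19) give endpoint SDs of 7.1 to 8.9; with an assumed baseline-to-endpoint correlation of 0.5, the SD of change is about 8.0. Power = Φ(δ√(n/2)/SD − 1.96):

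| p | Removed are missing | All 100 per arm measured |
|---|---|---|
| 10% | δ = 4.0, n = 90: 99.8% (SD 5.6), 91.8% (SD 8.0) | δ = 3.6, n = 100: 99.5%, 88.9% |
| 20% | δ = 4.0, n = 80: 99.5%, 88.5% | δ = 3.2, n = 100: 98.1%, 80.7% |

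The point itself does not depend on the power figure.

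**The case against.** The strongest reply is that nothing here is a contradiction. The withdrawal section governs conduct and Study Populations governs analysis; a removed participant stays in the ITT set. That is correct. A reader might infer that the two sections define incompatible populations, but the text does not support that. The problem is a possibly missing outcome.

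A reader might also infer that the primary comparison becomes one of compliers. The documents do not support this either. Removal is permitted, not required. The 80% threshold for the second set suggests that poor compliers are expected to remain with data. Anyone not removed is analysed with the score obtained.

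A third reply is that the plan already intends to retrieve people who stop early. That intent is real, and if the Retrieved Dropout Visit collected the CVLT-II, reason (d) would not by itself cost the outcome. But its content is not given, and the other visit excludes the test. So this point cannot be separated from what the dropout visits collect.

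Finally, it is tempting to cite the pilot's anxiety (2 of 18) and echolalia (1 of 18) on memantine as evidence that the drug would drive removal under (d). These are adverse experiences and fit reason (a) better. Removal that differs by arm is possible but not shown, and the direction of bias would then be unknown.

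**Conclusion.** The concern holds in a limited form. Reason (d), a single post-baseline CVLT-II, no stated CVLT-II after withdrawal and permitted replacement together mean that the primary ITT analysis may lack week-16 outcomes for non-adherent participants. The estimate can shift toward adherent participants, and ITT becomes a weaker check on the efficacy-evaluable result.

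The size cannot be fixed from the documents, which give neither a non-compliance rate nor a removal rate. The 5%, 11% and 25% figures are an illustrative upper case, not a forecast. They need every non-complier to be removed, exactly zero effect in them (although below 80% compliance is not zero exposure), and equal removal by arm. The 20% scenario has no basis in the documents. The plan should be changed because the remedy is cheap and the loss cannot be repaired later.

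**What to change.** Amend Withdrawal of Research Participants to separate stopping study drug from leaving follow-up, and state that:

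1. Non-compliance or a protocol violation is recorded and is not in itself a reason to end outcome follow-up.
2. Such participants are asked to complete the week-16 CVLT-II, at Visit 4 or at a Retrieved Dropout Visit whose listed content includes it, unless consent is withdrawn or the investigator judges that there is a safety reason not to.
3. A participant who is replaced stays in the ITT analysis in the arm to which they were randomised.
4. The 80% compliance rule applies to the efficacy-evaluable set only.

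Decisions about study drug and about safety-related removal stay with the sponsor and are not touched by this change.

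The cost is a short amendment. The week-16 visits are already scheduled; the only possible addition is the CVLT-II at the Retrieved Dropout Visit. The ITT effect may be somewhat smaller than an estimate from adherent participants alone, with the modest loss of power shown above under those assumptions.

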 - 1. If the research involves drugs or device(s), describe your plans to store, handle, and administer those drugs or device(s) so that they will be used only on research participants and be used only by authorized investigators.

UIP will purchase commercial grade memantine (Namenda®) from Forest Pharmaceuticals, Inc., bulk pack, and ship memantine and placebo to our Investigational Drug Services (IDS) at University Hospitals of Cleveland Case Medical Center (run by [name] R.Ph.). At IDS, the double-blind label bottles of medication will be filled by [name] and dispensed by a study coordinator at the site of the trial. The study dosages of memantine and placebo will be individually packaged and labeled.

Additionally, UIP will also perform all the individual packaging, double-blind labeling, and shipping to the São Paulo site. Packaging of the study dosages scheme for memantine and placebo will be identical to the one described above IDS at University Hospitals of Cleveland Case Medical Center. [name], R.Ph., Director, Non-Sterile Manufacturing and Maintenance for UIP will be in charge of all packing and labeling procedures related to the São Paulo site.

- 2. How will the drug(s) be dispensed (i.e., indicate the pharmacy that will be used)? Uh Hospitals Investigational Drug Services in the Cleveland site. [name], R.Ph., Director, Non-Sterile Manufacturing and Maintenance for UIP will be in charge of all packing and labeling procedures related to the São Paulo site.
 - 3. If the drug is investigational (has an IND) or the device has an IDE or a claim of abbreviated IDE (non-significant risk device), identify the holder of the IND/IDE/Abbreviated IDE

N/A

HRP-503BIO	TEMPLATE: Biomedical Protocol		
Approved:	05/11/2018	Prior Version:	1/23/2018

Additional Information

International information

1. São Paulo

If you have any additional information regarding your study not covered in the template, please include it here.

Community-Based Participatory Research

☐ This is not a community-based participatory research project – *please leave rest of this section blank*

If applicable, describe the involvement of the community in the design and conduct of the research.

APPENDIX 1 (Study Advertisement)

APPENDIX 2 (Subject Consent Forms)

APPENDIX 3 (case report form (CRF))

APPENDIX 4 (serious adverse event (SAE) reporting and FDA form 3500A - Medwatch)

APPENDIX 5 (Namenda® package insert)

PPENDIX 6 (Copy of the published article describing the results of the pilot study of memantine in young adults with Down syndrome)

Please reference the Investigator Manual for local institutional requirements.
